4.1 Inclusion Criteria

1. Only female patients are eligible
2. Patients must be 18 years of age or older
3. Patients must have Androgenic Alopecia Grade I-II by Ludwig Classification

4. Patients must have been on stable birth control for the past month if premenopausal.
5. Patients are able and willing to provide written informed consent after the nature of the study is fully explained

4.2 Exclusion Criteria

1. Patients with clinically abnormal hematology, serum chemistry, or screening laboratory results as reviewed by the Principal Investigator
2. Patients who have undergone topical and systemic therapies for hair loss 3 months prior to the procedure
3. Patients who have used any cosmetic product meant to address hair loss 3 months prior to enrollment
4. Patients taking anti-rheumatic disease medication (including methotrexate or other anti-metabolites) within the 3 months prior to study entry.
5. Patients previously having undergone hair transplant surgery prior to study entry
6. Patients who are pregnant or currently breast-feeding children as Rogaine for Women is contra indicated for these women
7. Patients who have taken spironolactone in the 3 months prior to study participation
8. Patients with systemic, rheumatic or inflammatory disease or who are immunosuppressed
9. Patients with ongoing infectious disease, including HIV and hepatitis
10. Patients with clinically significant cardiovascular, renal, hepatic, endocrine disease, cancer, or diabetes
11. Patients participating in a study of an experimental drug or medical device within 30 days of study entry
12. Patients with history of platelet disorders, bone marrow aplasia
13. Patients with a history of sepsis, or cancer must have been disease free for the past 5 years.
14. Patients taking antiaggregating therapy
15. Patients on anticoagulant therapy
16. Patients with tendency to keloid formation
17. Patients with uncompensated diabetes
18. Patients with active skin disease or skin infection at intended treatment areas

4.3 Subject Recruitment, Enrollment and Screening

Subjects will be recruited from the clinical practice of the Department of Dermatology, Mayo Clinic Florida. Patients seeking treatment for Androgenic Alopecia will be offered standard conservative medical therapy for their disease as part of routine dermatological treatment. As an alternative, patients will be informed of the study protocol, and offered the option to enroll if they meet the study eligibility criteria.

4.4 Early Withdrawal of Subjects

4.4.1 When and How to Withdraw Subjects

Subjects may withdraw from the study at any time for the following:

- Subject safety issues
- Subject decision to withdraw from the study (withdrawal of consent)
- Subject's decision to pursue other therapeutic regimens, either surgical or non-surgical

4.4.2 Data Collection and Follow-up for Withdrawn Subjects

Even though a subject has withdrawn from the study, it may be important to collect some follow-up or survival data on subjects throughout the protocol defined follow-up period. Such data are important to the integrity of the final study analysis since early withdrawal could be related to the safety profile of the study drug. If a subject withdraws consent to participate in the study for subject safety reasons attempts will be made to obtain permission to collect follow up information whenever possible. Patients will be analyzed by intention to treat principles without some of the follow-up data as necessary.

5 Study Drug

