7.1 Sample Size Determination

A total of 23 patients will be enrolled in this study. This sample size will be sufficient in order to gain valuable data to be used in the design of a future, larger study. Given the pilot/feasibility nature of the study, no formal power calculations were performed.

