7.2 Statistical Methods

Data Analysis – Given the design, all statistical analysis will be focused on the difference in outcomes, and differences in outcomes compared to baseline, for each treatment within individual patients. For continuous or ordinal outcome variables, we will use a Wilcoxon signed rank test for comparison of outcomes between PRP and Minoxidil, while for categorical outcome variables we will use McNemar's exact test for these. Continuous outcome measures will be summarized using the sample mean, standard deviation, median, minimum, 25th and 75th percentiles, and maximum. Categorical variables will be summarized with number and percentage. 95% confidence intervals (CIs) will be estimated where appropriate. P-values of 0.05 or less will be considered as statistically significant, however the results of these tests will be interpreted with the low power of this pilot study in mind; more emphasis will be placed on graphical and descriptive summaries than on the results of statistical tests. No adjustment for multiple testing will be made owing to the exploratory, pilot nature of the study. Given the prospective nature of the study, we expect to encounter little if any missing data. However in the event of missing data, no attempt to impute this missing data will be made in this pilot study; missing data will be treated as missing.

Descriptive Statistics

We will summarize continuous variables using the sample mean, standard deviation, median, minimum, 25th and 75th percentiles, and maximum. We will summarize categorical variables with number and percentages. Ordinal variables will be summarized using the sample median, minimum, 25th and 75th percentiles, and maximum, as well as with number and percentage.

Handling of Missing Data

Given the prospective nature of the study, we expect to encounter little if any missing data. However in the event of missing data, no attempt to impute this missing data will be made in this pilot study; missing data will be treated as missing.

Multiplicity

No adjustment for multiple testing will be made owing to the exploratory, pilot nature of the study. P-value of 0.05 or less will be considered as statistically significant.

Primary Hypothesis:

We hypothesize that PRP administration for AGA will be safe and without significant complications for the patient. AGA will be comparable in efficacy or superior to conventional treatment with MNX.

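### The one operative follow-up step in section 4.4.2 covers safety withdrawals, so some adverse events in other leavers have no active collection step

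*Combined protocol and SAP*

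**What the plan says.** Section 4.4.1 gives three grounds for leaving: safety issues, the subject's own decision (withdrawal of consent), and "Subject's decision to pursue other therapeutic regimens, either surgical or non-surgical".

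Section 4.4.2 opens by saying that data on withdrawn subjects may be important, because "early withdrawal could be related to the safety profile of the study drug". That rationale is not tied to a particular ground. The next sentence sets the action: where a subject withdraws consent "for subject safety reasons attempts will be made to obtain permission to collect follow up information whenever possible". The section then calls for intention-to-treat analysis, accepting that some follow-up data will be absent.

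Section 7.2 names adverse reactions and morbidity as dichotomous primary endpoints, to be reported as proportions with 95% confidence intervals and compared between treatments by McNemar's exact test. On missing values it says "we expect to encounter little if any missing data", rules out imputation, and adds that "missing data will be treated as missing". Section 7.1 fixes the size: "A total of 23 patients will be enrolled in this study", and "no formal power calculations were performed".

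**The concern.** The action in 4.4.2 is narrower than the reason given for it. If leaving early may signal a safety problem, the signal can also be present when the recorded ground is something else. Section 5.4 implies about 100 injection sites per PRP session (10 cc at 0.1 cc per site), section 3.4 makes injection-site pain a safety endpoint, and section 5.5 bars other hair-loss therapy during the study. A subject who tolerates treatment poorly could therefore plausibly be recorded as having changed her mind or moved to another treatment.

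Whether her later events are sought then depends on a label that may itself be related to tolerability. That makes the missing safety data potentially informative, and the plan has no later step that would correct for it. The estimates at stake are the single-treatment adverse-event proportions, which matter most in a pilot that puts descriptive summaries ahead of tests.

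**Working it through.** The plan gives no withdrawal rate, adverse-event rate or power calculation, so there is no figure to reproduce. The check is a comparison of sections, followed by arithmetic on assumed counts.

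**Which events does some other section capture in a subject who leaves for a non-safety reason?**

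| Event | Provision | Captured? |
|---|---|---|
| Recorded before leaving | 8.2 requires all events in the study period to be recorded; 9.2 keeps data collected before authorization is revoked | Yes |
| Known and unresolved at leaving | 8.1 (Post-study Adverse Event) follows it, with no condition on the reason for leaving | Yes, but how this works after consent is withdrawn is not stated |
| Occurred before leaving, but before the first scheduled check | 8.2 requires questioning at each contact; no withdrawal contact is defined | No active step |
| Arises after leaving | 9.2 seeks permission for at least vital status, and only after authorization is revoked | No active step for adverse events |

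**How long is the window before the first check?** From section 6 item d and the 6.1 calendars:
- PRP: first check 1 week after each injection.
- Minoxidil in Arm B: start at baseline, first check at Week 12.
- Minoxidil in Arm A: start at Week 20, next check at Week 32, so 32 − 20 = 12 weeks.

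**Size per subject.** If N subjects received a treatment, x events were observed, and k leavers with no recorded event were not followed, the true proportion lies between x/N and (x + k)/N. The width is k/N. With N = 23, each subject adds 1/23 = 4.3 points. If fewer received that treatment the step is larger; for example, 1/20 = 5.0 points.

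Illustration, assuming x = 2 and N = 23 (Clopper-Pearson intervals):
- Lower bound: 2/23 = 8.7% (95% CI 1.1% to 28.0%).
- Upper bound, k = 1: 3/23 = 13.0%.
- Upper bound, k = 2: 4/23 = 17.4%.
- Upper bound, k = 3: 5/23 = 21.7%.
- Upper bound, k = 5: 7/23 = 30.4% (95% CI 13.2% to 52.9%).

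**Dependence on the label.** Assume 19 completers with 2 events, and 4 leavers who each have an event not yet recorded. Let s of the 4 be classed as safety withdrawals and agree to follow-up, and let the rest drop out of the denominator. The reported proportion is (2 + s)/(19 + s):
- s = 0: 2/19 = 10.5% (95% CI 1.3% to 33.1%).
- s = 2: 4/21 = 19.0%.
- s = 4: 6/23 = 26.1% (95% CI 10.2% to 48.4%).

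If unfollowed leavers instead stay in the all-treated denominator as having no event, the same cases give 2/23 = 8.7%, 4/23 = 17.4% and 6/23 = 26.1%. Either way the clinical facts are identical and only the label differs.

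**Paired test.** For m discordant pairs all in one direction, the two-sided exact p-value is 2 × 0.5^m: 0.0625 for m = 5 and 0.031 for m = 6. One pair can therefore cross the threshold in section 7.2 ("P-value of 0.05 or less will be considered as statistically significant"). A subject who leaves before her second treatment forms no pair whether or not she is followed, so only second-period leavers can matter here.

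**The case against.** The strongest reply is that most of what matters is already collected. Local PRP reactions are expected within 2 to 3 days (section 1.4). Adverse events and injection sites are checked one week after every injection, and adverse events again at the next injection visit. Section 8.2 requires specific questioning at each contact. A subject who leaves because the injections hurt has usually had that pain recorded before or as she leaves. This stands, and it limits the PRP gap to subjects lost before the Week 1 check and to events that begin after leaving. It helps less on minoxidil, where the first check comes 12 weeks after the start.

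A reader might infer that all adverse events in non-safety leavers are lost. The documents do not support this: recorded events are retained, and known unresolved events are followed under 8.1 whatever the reason for leaving. A reader might also infer that other leavers may not be approached. Nothing in 4.4.2 forbids it, and its opening sentence covers withdrawn subjects generally; what is missing is a step that requires it. Nor does the section say that every early withdrawal reflects safety (it says this could be so), or that the subject's own words decide the classification. An investigator could class intolerable pain as a safety reason. Finally, 9.2 sets vital status as a minimum, not a ceiling.

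It is also fair to say that this is an unpowered pilot that expects little missing data. That lowers the stakes but does not remove the mismatch between rationale and action.

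**Conclusion.** The point holds as a limited gap in a stated rule. Section 4.4.2 actively seeks follow-up on a narrower basis than its own rationale and than the three routes in 4.4.1. In subjects who leave for other recorded reasons, events after withdrawal and events before the first scheduled check have no active collection step. With no imputation, the single-treatment adverse-event proportions can then vary with the recorded reason for leaving. The McNemar comparison is less exposed.

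The size cannot be stated, because no withdrawal rate is given. The firm figure is the step of up to 4.3 points per unobserved subject on a denominator of 23. The ranges above rest on assumed counts and on leavers contributing no recorded event, so they are outer bounds and should not be read as expected bias. The confidence intervals at this sample size are already wide. This is a cheap improvement, not a flaw that undermines the trial.

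**What to change.** - In section 4.4.2, strike the four-word qualifier that limits the step to safety reasons, so that permission for follow-up is sought from every subject who withdraws.
- State that adverse events are asked about at the withdrawal contact. Section 8.2 already requires this at each contact; the change makes the withdrawal contact explicit and closes most of the gap before the first scheduled check.
- Reconcile 4.4.2 with 8.1 (following unresolved events), 8.2 (recording all events) and 9.2 (permission after authorization is revoked), so that the same request applies in each place.

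The cost is a wording change plus one extra request or contact for each subject who leaves. Subjects may still refuse or be lost, so reporting the number not followed, by treatment and recorded reason, would let readers apply the bounds above.

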5.1 Description

1. PRP – Autologous Platelet Rich Plasma isolated from blood collected from each patient at each treatment time point.

2. Minoxidil 5% Topical Foam - Manufacturers Description: Indications: To regrow hair on top of the scalp. Active Ingredient: Minoxidil 5% w/w (without propellant) Inactive Ingredients: butane, butylated hydroxytoluene, cetyl alcohol, citric acid, glycerin, isobutane, lactic acid, polysorbate 60, propane, purified water, SD alcohol 40-B, stearyl alcohol (Rogaine for Women).

5.2 Treatment Regimen

Patients will be randomized into a PRP then MNX (Arm A) or MNX then PRP group (Arm B). Patients randomized to Arm A will receive injections of PRP using the nappage technique (Sivagnanam) every 4 weeks for a total of 3 treatments over 12 weeks. Patients will then have a 2 month (8 week) washout period lasting until the end of month 4. Starting on month 5 they will receive crossover treatment with Minoxidil by applying the 5% foam once daily following manufacture instructions (Rogaine For Women) for a total of 3 months after which they will be followed until 1 year after enrollment. Patients randomized to Arm B will apply Minoxidil topical foam once daily following manufacture instructions for a total of 3 months followed by a two month (8 week) washout period. At the 5 month mark, the patients in Arm B will receive crossover treatment with PRP harvested and administered in the same manner as the patients in Arm A. At the end of the PRP treatment patients in Arm B will be followed until 1 year after enrollment.

5.3 Method for Assigning Subjects to Treatment Groups

Assignment of treatments will be randomized using dynamic allocation.

5.4 Preparation and Administration of Study Drug

PRP will be harvested and prepared in the Mayo Jacksonville Dermatology practice. 20 mLs of blood will be collected from patients using standard venipuncture technique. Collected blood will be processed using a standard dual spin centrifugation protocol resulting in approximately 10.5 mLs of PRP. The 10 cc of PRP will be injected with a 30-gauge needle using the nappage technique (Sivagnanam) over the affected part of the scalp, approximately 1/10 cc / injection site. At the investigators discretion scalp may be numbed with Gebauer's Pain Ease Nonflammable Medium Stream Spray Instant Topical Anesthetic or Impax Lidocaine and Prilocaine Cream, USP 2.5%. The remaining 0.5 mL of PRP will be collected for future research purposes.

5.5 Prior and Concomitant Therapy

Subjects will not be allowed any concomitant therapy for hair loss treatment.

No prior hair replacement / treatment surgeries.

No topical and systemic therapies for hair loss 3 months prior to study enrollment.

6 Study Procedures

- a.** At baseline all patients will undergo a clinical exam, assessments of hair density using phototrichograms, macroscopic photographs, patient questionnaires and labs including CBC, ferritin, thyroid function, testosterone, TSH and pregnancy test for premenopausal women. All patients will also have a small area shaved at the center of the treatment area, as well as a small tattoo injection to allow for follicle counting via the computerized software.
- b.** At 3 months, 5 months, 8 months and 12 months, patients will have repeat clinical exams and phototrichograms, macroscopic photographs and complete patient questionnaires.
- c.** At 12 months, repeat serum tests (CBC, ferritin, thyroid function, testosterone, TSH) will be performed.
- d.** Adverse events will be assessed at each visit (3, 5, 8 and 12 months post enrollment) as well as 1 week after each injection of PRP.
- e.** Shampoo and conditioner will be standardized with the study supplying Free & Clear brand products to the patients free of charge for the duration of the study.
- f.** Pre-menopausal patients will undergo a second pregnancy test before beginning the cross-over treatment.

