CRF	Case Report Form
DSMB	Data and Safety Monitoring Board
FDA	Food and Drug Administration
GCP	Good Clinical Practice
HIPAA	Health Insurance Portability and Accountability Act
IB	Investigator's Brochure
IRB	Institutional Review Board
MNX	Minoxidil
PHI	Protected Health Information
PI	Principal Investigator
PRP	Platelet Rich Plasma
SAE	Serious Adverse Event/Serious Adverse Experience
SOP	Standard Operating Procedure

Study Summary

Title	Minoxidil Foam compared to PRP for Androgenic Alopecia in Women, A Randomized Controlled Pilot Trial
Running Title	PRP for Hair loss in Women
Protocol Number	1
Phase	Pilot
Methodology	Randomized, Controlled, Crossover
Overall Study Duration	12 Months
Subject Participation Duration	12 months
Single or Multi-Site	Single Site
Objectives	Determination of non-inferiority treatment of PRP compared to standard of care MNX in women
Number of Subjects	23
Diagnosis and Main Inclusion Criteria	Female, 18 years or older, Androgenic Alopecia grade I-II by Ludwig classification
Study Product, Dose, Route, Regimen	Platelet Rich Plasma 10cc, Injection by Nappage technique, 3 injections - 1 time every 4 weeks for 3 months
Duration of Administration	12 Weeks (1 time every 4 weeks for 3 months)
Reference therapy	Minoxidil
Statistical Methodology	Wilcoxon signed rank test for comparison of outcomes between treatments and McNemar's exact test for categorical outcome variables

1 Introduction

This document is a protocol for a human research study. This study will be carried out in accordance with the applicable United States government regulations and Mayo Clinic research policies and procedures.

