1.4 Dose Rationale and Risk/Benefits

We will dose PRP in a manner similar to previous trials. (Gentile, Trink, Cerveli) Fresh PRP will be harvested from the individual and their own PRP administered at three time points, once every 4 weeks for a totally treatment time of 12 weeks. Minoxidil will be used according to FDA and manufacturer instructions daily for 12 weeks.

Risks associated with PRP therapy include possible pain, redness, and/or irritation at the site of injections for up to 2-3 days post injection. Published human data indicate no significant adverse events related to injection of PRP into the skin and previous authors utilizing similar protocols reported no infection, fever, hematoma, tissue hypertrophy, or major adverse events among the subjects. (Singhal) (Cerveli) (Gentile) (Trink) (Gkini) Known possible risks for Minoxidil include chest pain, rapid heartbeat, faintness, dizziness, sudden or unexplained weight gain, swelling of the hands or feet, scalp irritation or redness, changes in hair color and texture, and unwanted facial hair growth.

[figure not shown]
2 Study Objectives

The overall goal of this study is to develop regenerative cell therapy for use in female patients with AGA. The primary objective of this proposal is to conduct a pilot study on the efficacy of using PRP to treat this type of hair loss in females.

3 Study Design

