3.1 General Design

The study will be a randomized control trial following a crossover design to compare PRP to MNX in females.

Subjects will be recruited from the clinical practice of the Department of Dermatology, Mayo Clinic Florida. 23 females with AGA grades I-II based on the Ludwig Classification. (Ludwig)

Patients will be randomized into a PRP then MNX (Arm A) or MNX then PRP group (Arm B). Both treatments will be administered for 12 weeks with a 2 month washout period in between treatments. Hair density and adverse events will be assessed using Phototrichograms, Macroscopic Photos, physical exams and patient questionnaires. All patients will be followed for efficacy and adverse events at 3 month intervals until 1 year after enrollment.

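### The protocol provides for no masked reading of the hair images in a comparison that is open-label in effect, so image-based hair outcomes are open to expectation bias

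*Combined protocol and SAP*

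**What the plan says.** **Design.** The methodology row of the Study Summary reads "Randomized, Controlled, Crossover". Section 3.1 says "The study will be a randomized control trial following a crossover design to compare PRP to MNX in females". Section 5.3 says "Assignment of treatments will be randomized using dynamic allocation". None of the three gives a masking level.

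**Treatments.** Under Section 5.2, patients in Arm A "will receive injections of PRP using the nappage technique (Sivagnanam) every 4 weeks for a total of 3 treatments over 12 weeks", and patients in Arm B "will apply Minoxidil topical foam once daily following manufacture instructions for a total of 3 months". Each group then crosses over. No sham injection or placebo foam is described.

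**Hair outcomes.** Section 3.1 says "Hair density and adverse events will be assessed using Phototrichograms, Macroscopic Photos, physical exams and patient questionnaires". Section 6, item b, says that at months 3, 5, 8 and 12 "patients will have repeat clinical exams and phototrichograms, macroscopic photographs and complete patient questionnaires". Item a plans the same assessments at baseline and adds a shaved, tattooed target area in which follicles are counted by software.

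**Status of the outcome.** Section 3.2 lists hair growth first among the primary endpoints. Section 7.2, under the primary hypothesis, names only adverse reactions and morbidity as primary.

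**Analysis.** Section 7.2 compares continuous and ordinal outcomes within patient by the Wilcoxon signed rank test at 0.05, and gives descriptive and graphical summaries more weight than tests. Section 7.1 sets 23 patients without a power calculation.

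**The concern.** A course of scalp injections and a daily foam cannot be mistaken for each other, so the patient and the treating staff know which treatment was given. In such a trial, the usual safeguard for an imaging outcome is a reader who does not know the treatment. The protocol has no such step. If it is followed as written, nothing prevents the images from being assessed by someone who knows the arm and the visit.

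The direction of expectation is not neutral. The stated hypothesis is that PRP does as well as minoxidil or better, and the Study Summary gives non-inferiority as the objective. A lean toward PRP in the readings would make that conclusion easier to reach and could hide a true disadvantage. The results are also meant to inform a larger trial, so a biased estimate would carry into its design. Section 1.3 itself criticises earlier PRP studies for inconsistent evaluation methods and calls for standardised measurement.

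**Working it through.** **1. Is masked reading provided for anywhere?** Sections 3.1, 5.2, 5.3, 6, 6.1 and 7.2 give the instruments, visits and tests. None mentions blinding, coded images or an independent reader, and none names the person who reads the images. Section 9.1 has the study coordinator collect and enter data, which does not say who assesses images. The plan is therefore silent; it does not state that reading is unmasked.

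**2. Which hair measures are exposed?**

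| Measure | What the protocol says | Exposure |
|---|---|---|
| Phototrichogram follicle count | Software, on a marked area; manual steps not described | Limited, unless an operator selects or corrects |
| Macroscopic photographs | No scoring method given | Greatest among the image outcomes |
| Physical examination, questionnaires | Done with patient and staff aware of treatment | Cannot be masked by coding images |

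**3. Would arm, visit and treatment be separable?** From the Section 6.1 calendars:

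| | Arm A | Arm B |
|---|---|---|
| PRP injections | Baseline, weeks 4, 8 | Weeks 20, 24, 28 |
| Images at end of PRP | Week 12 | Week 32 |
| Gap from last injection | 12 − 8 = 4 weeks | 32 − 28 = 4 weeks |
| Images at end of minoxidil | Week 32 | Week 12 |
| Images on an injection day | Baseline | Week 20 |

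Week 12 ends PRP in one arm and minoxidil in the other, so visit and sequence together reveal the treatment; both must be hidden. Section 1.4 puts PRP "irritation at the site of injections for up to 2-3 days post injection", well inside the 4-week gap. The same section lists scalp redness and altered hair colour or texture as possible minoxidil effects, and the end-of-minoxidil images fall at the close of daily use. On the two injection-day visits, images must precede the injection to avoid showing it.

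**4. Illustrative size.** The plan has no figure of its own to reproduce. Inputs:
- n = 23 (Section 7.1).
- Signed-rank test at 0.05 (Section 7.2), two-sided by assumption because sidedness is not stated.
- True difference zero, and normal paired differences with SD 1 (assumptions).
- A constant reading shift of b SDs toward PRP (assumption; the documents give neither an SD nor a reader error).

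The rank sum ranges from 0 to 23 × 24 / 2 = 276. Under the exact null distribution, the two-sided test rejects at 73 or below, or at 276 − 73 = 203 or above. Its exact size is 0.048. Rejection rates from 200,000 simulated trials:

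| b (SD) | Any rejection | Rejection favouring PRP |
|---|---|---|
| 0 | 0.049 | 0.024 |
| 0.1 | 0.071 | 0.063 |
| 0.2 | 0.143 | 0.141 |
| 0.3 | 0.265 | 0.265 |
| 0.4 | 0.430 | 0.430 |
| 0.5 | 0.608 | 0.608 |

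As a rough cross-check, a two-sided normal test with known SD, Φ(b√23 − 1.96) + Φ(−b√23 − 1.96), gives 0.160, 0.301 and 0.669 at b = 0.2, 0.3 and 0.5. These are somewhat higher, but follow the same pattern.

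**5. Effect on the descriptive summaries.** The mean paired difference moves by b. Its standard error is 1/√23 = 0.209 SD, so shifts of 0.2, 0.3 and 0.5 SD equal 0.2/0.209 = 0.96, 0.3/0.209 = 1.44 and 0.5/0.209 = 2.39 standard errors.

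**The case against.** **Silence is not evidence of unmasked reading.** This stands. A reader might infer that the team giving PRP will read the images knowing treatment, period and visit. The documents do not support that, because no reader is named. What they support is that nothing requires masked reading.

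**The count is by software.** This stands in part. A software count on a tattooed area leaves less room for expectation, but the protocol does not say whether it is fully automatic. The photographs have no such safeguard. They also have no defined score, so the way they would be graded is itself unspecified.

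**Hair growth may not be primary.** Sections 3.2 and 7.2 disagree on this. Coding images does nothing for the safety endpoints that Section 7.2 names. Even so, the efficacy comparison appears in the objectives and the hypothesis, so its images matter under either list.

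**It is a pilot, and tests carry little weight.** The false-positive rate is indeed not the main quantity here. But a reading shift moves medians, plots and confidence intervals as well as p-values, so the emphasis on description gives no protection.

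**The shifts are arbitrary.** This stands. Nothing in the documents supports 0.2 to 0.5 SD, least of all for a software count, and 0.5 SD is not small. The rates illustrate sensitivity and should not be taken as evidence of how severe the problem is.

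**Coding would not fully mask.** This also stands. It is tempting to infer from the brief PRP skin reaction that the images cannot reveal treatment, but the minoxidil effects listed in Section 1.4 could be visible. Staff taking the images would also still know the treatment.

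**Conclusion.** The concern holds as a gap in specification with a practical remedy. The comparison is open-label in effect. The protocol provides for no masked reading and names no reader, and image-based hair outcomes are open to expectation bias as a result. The exposure is clearest for the macroscopic photographs and for any manual step in the follicle count.

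Its size is unknown. If the true difference were zero, an assumed shift of 0.2, 0.3 or 0.5 SD would take the false-positive rate from about 5% to about 14%, 27% or 61% at n = 23, given normal paired differences and a two-sided test. If masked reading removed the shift entirely, the rate would return to the test's exact size of 0.048. A reader might infer that coding images would prevent bias in the hair outcome as a whole. It would not: examinations and questionnaires stay open, image acquisition stays unmasked, and masking of the images may be incomplete. The change is still worth making, because it uses images already planned and leaves the sample size alone.

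**What to change.** Add to Section 6:

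- The comparison is open-label for patients and treating staff. The protocol names who runs the follicle count and who assesses the photographs, by role, states any manual step in the count, and gives the scoring method for the photographs.
- At a visit with a PRP injection, images are taken before the injection.
- The study coordinator exports phototrichograms and macroscopic photographs under random codes, without patient, arm, date or visit.
- Whoever runs the count and assesses the photographs works through the coded images in random order. The code is broken only after the readings are entered in REDCap.
- Examinations and questionnaires are reported as open-label, and the report notes that minoxidil effects on scalp or hair may have revealed treatment on some images.

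**Cost.** The coordinator codes about 23 × 5 = 115 image sets, and reading waits until images are batched. No additional patients, visits, procedures or readers are needed.
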